#### 4.2 Exclusion Criteria

- Type 1 diabetes, gestational diabetes and other special types of diabetes
- Poor blood glucose control, HbA1c > 8.5% within 3 months
- Taking antidiabetic drugs in the past month
- Serum ALT > 6 times of normal upper limit
- Excessive alcohol consumption (alcohol intake: men > 140 g, women > 70 g in the past 6 months)
- Other liver diseases: such as acute and chronic viral hepatitis, drug-induced hepatitis, immune hepatitis, liver cirrhosis, liver cancer, etc
- Taking drugs that may affect MASLD in the past three months, such as vitamin E
- Biliary obstructive diseases
- Other diseases affecting glucose and lipid metabolism: hyperthyroidism, hypothyroidism, Cushing's syndrome, etc
- Chronic kidney disease (serum creatinine ≥ 2.0 mg/dL)
- Life expectancy of no more than 5 years
- Already pregnant or plan to be pregnant in the near future
- Mental illness
- Other conditions affecting follow-up

[figure not shown]
- Have participated in other clinical trials in the past 4 weeks
- Absent of informed consent

4.3 Termination criteria

- Request to withdraw informed consents
- Pregnancy
- Systolic blood pressure ≥ 180 mmHg and diastolic blood pressure ≥ 110 mmHg
- Liver enzymes (ALT or AST) increase to ≥ 6 times of the upper normal limit and last for 4 weeks
- Fasting blood glucose increases to > 200 mg/dL and lasts for 4 weeks
- Serum creatinine increases to ≥ 1.5 mg/dL
- During the treatment, drugs which may affect liver fat content are added or adjusted for dosage: such as hypoglycemic drugs, lipid-lowering drugs and liver protecting drugs
- 5. Intervention

After a 2-week screening phase, a total of 60 eligible patients will be randomized 1:1 into ICR and CCR group.

Figure 1. Study design

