6.3 Other pre-specified outcomes

- Change of fat mass and lean mass measured by a bioimpedance analyzer
- Change of abdominal adiposity measured by MRI: visceral adipose tissue and subcutaneous adipose tissue
- Change of liver stiffness measured by liver transient elastography
- Change of insulin sensitivity: fasting insulin and HOMA-IR (fasting glucose in mmol/L x fasting insulin in  $\mu$ U/mL)/22.5)
- 7. Follow-up visits
- (1) Screening visit (V0): The purpose of this visit is to confirm subjects' eligibility and interest in the proposed study, and obtain informed consent, relevant medical history (including diabetes, fatty liver, alcohol drinking history, hepatitis history, drug use, etc.), physical measurements (weight, height, waist circumference and blood pressure), and laboratory measurements (OGTT, HbA1c, liver and renal functions, electrolytes, hepatitis markers, etc). H-Proton Magnetic Resonance Spectroscopy (H-MRS), MRI-Proton Density Fat Fraction (MRI-PDFF) and liver transient elastography were applied to evaluate the fatty liver. Body composition analysis and other examinations were performed. Relevant laboratory and imaging examination results within 2 weeks before screening can be approved.
- (2) Baseline visit (V1): The baseline follow-up was scheduled within 2 weeks after the screening period. Physical examination was conducted. Subjects will be required to record their diet and steps for 3 days before day 0 and the average of calorie consumption and steps will be used as baseline reference. Randomization will be conducted.
- (3) Follow up and termination visits (V2 V9): At each visit, diet and step records will be collected. At week 2, 4, 8 12, physical measurements, fasting glucose and adverse events will be recorded. Nutritionists will provide dietary advice and help subjects to keep calorie

restriction and a balance of nutrients. On this basis, liver and renal functions, electrolytes, fasting blood glucose and lipids profiles will be measured at week 4. At week 12 (termination visit), OGTT, H-MRS, MRI-PDFF, liver transient elastography and body composition analysis will be added. At week 1, 3, 6, 10, only telephone follow-up will be conducted.

(4) Post-intervention visit (V10): At 4 weeks after the intervention (week 16), body weight will be investigated by telephone.

	Screening	Baseline								Termin ation	Post- interve ntion
Visit	V0	V1	V2	V3	V4	V5	V6	V7	V8	V9	V10

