Physical measurements: At the clinic visit, trained staff will take measurements of body weight, height, waist circumference, blood pressure according to standard procedures. Subjects should avoid wearing shoes and heavy clothes when measuring body weight. Mid-way between the lower border of rib margin and the upper border of iliac crest will be measured as waist circumference. The blood pressure will be measured after resting for 5 minutes in a sitting position and alcohol, cigarettes, coffee/tea and physical exercise will be avoided within 30 minutes before the measurement. Automatic sphygmomanometer will be applied for standardized detection.

Laboratory measurements: Blood samples will be drawn 10 hours after fasting and be used to measure blood glucose, HbA1c, liver enzymes, serum creatinine, urine acid and lipids.. High performance liquid chromatography (HPLC) method will be used for measuring HbA1c. Total cholesterol, high-density lipoprotein cholesterol, triglycerides, free fatty acids, electrolytes, liver enzymes, serum creatinine and urine acid will be measured by a model 7600 automated bioanalyzer (Hitachi, Tokyo, Japan). Low-density lipoprotein cholesterol will be calculated by the Friedewald equation. The FBG and 2-hour postprandial blood glucose in oral glucose tolerance test will be tested following a standard 75g oral glucose tolerance test and measured using the glucose oxidase method. An electrochemiluminescence immunoassay will be used to measure the fasting and 2-hour postprandial insulin. All parameters are tested in the clinical biochemical laboratory of Zhongshan Hospital affiliated to Fudan University. The clinical testing laboratory will adopt the standardized process and obtain the corresponding certification qualification.

H-MRS: Whole liver fat content by H-MRS was performed with a 1.5T MRI Scanner (Siemens Healthineers, Germany). Firstly, T1-weighted sagittal, coronal, and axial images were acquired for the localization of the spectroscopy acquisition voxel. A single 2×2×2 cm voxel was placed within the right lobe avoiding major vascular structures and subcutaneous fat tissue. The proton spectrum was acquired after shimming over the volume of interest by means of a point-resolved spectroscopy sequence with the following parameters: repetition time = 1500 ms and echo time = 135 ms. Signal intensities of the water peak at 4.8 ppm (Sw) and the fat

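### On scheduled tests, the 4-week ALT/AST stopping rule cannot be met before the week-12 termination visit for a rise first seen on treatment; separately, the creatinine stop limit (1.5 mg/dL) lies below the entry limit (2.0 mg/dL)

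*Combined protocol and SAP*

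**What the plan says.** **Liver rule.** Section 4.3 lists as a ground for termination: "Liver enzymes (ALT or AST) increase to ≥ 6 times of the upper normal limit and last for 4 weeks".

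**Test schedule.** Section 7 says that "liver and renal functions, electrolytes, fasting blood glucose and lipids profiles will be measured at week 4", and the list of additions for week 12 follows. The liver and renal functions row of Table 2 is marked at screening, week 4 and week 12 only. For the other clinic visits section 7 says: "At week 2, 4, 8 12, physical measurements, fasting glucose and adverse events will be recorded". No liver or renal panel is named there for weeks 2 or 8. Weeks 1, 3, 6 and 10 are telephone contacts. Week 12 is the termination visit.

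**Blood draws.** Table 2 also has a general blood-sample row, marked at weeks 0, 2, 4, 8 and 12. Section 8 says that blood samples will "be used to measure blood glucose, HbA1c, liver enzymes, serum creatinine, urine acid and lipids".

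**Creatinine.** The exclusion in 4.2 reads "Chronic kidney disease (serum creatinine ≥ 2.0 mg/dL". The termination criterion in 4.3 reads "Serum creatinine increases to ≥ 1.5 mg/dL", with no duration attached.

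**The concern.** A stopping rule with a duration needs two measurements that far apart, and the second must come early enough to matter. Here the second scheduled liver test falls at the visit where the 12-week diet ends. For a treatment-emergent rise, the rule as scheduled confirms the problem only when there is no intervention left to stop.

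The creatinine limits raise a different difficulty. A patient can be eligible with a value already at or above the level that defines termination. The text does not say how the rule applies to that patient, so two investigators could apply it differently.

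What is at stake is whether two stated safety rules can work as written. The power calculation and the primary estimate are not in question.

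**Working it through.** **Inputs (Table 2 and section 7).** Week 4 is day 28 ± 7, i.e. day 21 to 35. Week 8 is day 56 ± 7, i.e. 49 to 63. Week 12 is day 84 ± 7, i.e. 77 to 91. On-treatment liver and renal tests are at weeks 4 and 12.

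**Step 1: which pairs of scheduled tests could satisfy the liver rule?** With two on-treatment tests there is one pair, week 4 and week 12.
- Nominal gap: 84 − 28 = 56 days.
- Shortest gap: 77 − 35 = 42 days.
- Longest gap: 91 − 21 = 70 days.

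The earliest confirmation is therefore day 77 to 91, at the termination visit. The nominal wait is 56 of 84 intervention days. A rise first seen at week 12 has no later scheduled liver test. The result does not depend on whether 4 weeks means exactly 28 days, because no scheduled liver test lies between the two.

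The restriction to a rise first seen on treatment is needed. Section 4.2 excludes ALT only above 6 times the upper limit and sets no AST limit, so a high screening value could in principle be paired with week 4.

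**Step 2: do the week-2 and week-8 blood draws fill the gap?** Section 8 lists liver enzymes and creatinine among the assays. The same list names HbA1c, which Table 2 schedules only at screening and week 12. The list therefore says what is assayed and does not fix the visits. The specific Table 2 row and the section 7 text are the better guide.

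**Step 3: what would a week-8 panel gain?** Confirmation of a week-4 rise would move from week 12 to week 8: 84 − 56 = 28 days earlier nominally, and 77 − 63 = 14 to 91 − 49 = 42 days within windows. The week-4 to week-8 gap is 28 days nominally, but 49 − 35 = 14 to 63 − 21 = 42 within windows, so an unscheduled repeat may sometimes be needed. A rise first seen at week 8 would still be confirmed only at about week 12.

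**Step 4: creatinine.** Entry is allowed below 2.0 and the stop applies from 1.5, so the overlap is 2.0 − 1.5 = 0.5 mg/dL (1.5 to under 2.0). Take a patient who enters at 1.6.
- If any rise that ends at 1.5 or more counts, 1.6 to 1.7 terminates the patient.
- If only a crossing from below 1.5 counts, no rise from 1.6, however large, meets the rule.

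One scheduled on-treatment creatinine test (week 4) precedes the termination visit.

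**The case against.** **The rule does not demand scheduled tests.** Section 4.3 asks only that the elevation last 4 weeks. Patients attend in person at week 8 and blood is drawn. Section 8 limits metabolomics blood to weeks 0 and 12, so metabolomics does not explain the draws at weeks 2, 4 and 8. If enzymes were run on those samples, the rule could be met at week 8. This stands as a limit on the claim: the conclusion concerns what is scheduled, and the documents do not schedule enzymes at week 8.

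**Other routes can stop a patient earlier.** An investigator may repeat a test. The added-drug criterion in 4.3 covers treatments "such as hypoglycemic drugs, lipid-lowering drugs and liver protecting drugs". Section 9.3 stops the intervention for serious adverse events. A reader might infer that this last route is closed unless the event is judged definitely or probably related, because 9.2 counts only such events. The text does not support that: the stop in 9.3 has no relatedness condition, and 9.3 requires all serious events to be reported whether related or not. The definition in 9.1 does refer to causation by the intervention, so the wording is mixed. Section 9.1 also requires follow-up of unresolved events, including abnormal results, which helps with a rise first seen at week 12. What remains is that none of these routes sets a repeat enzyme test, and an enzyme rise without symptoms need not be a serious event.

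**A stop limit stricter than the entry limit can be deliberate.** Terminating a patient who goes from 1.6 to 1.7 is cautious rather than unsafe, and the crossing-only reading is not forced by the text. Both remarks are fair. The wording still leaves the choice open.

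**The glucose rule.** Since it has the same 4-week form, a reader might infer that it shares the defect. It does not: fasting glucose is scheduled at weeks 2, 4, 8 and 12, the nominal gaps from week 4 to 8 and from week 8 to 12 are 28 days, and shortfalls arise only at the edges of the visit windows.

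**Conclusion.** The point holds and is minor. For a treatment-emergent ALT or AST rise to 6 times the upper limit or more, the rule in 4.3 cannot be met on scheduled tests before the termination visit, 42 to 70 days after the week-4 test. For patients who enter with creatinine of 1.5 to under 2.0 mg/dL, the creatinine rule is either over-sensitive or, on a crossing-only reading, without effect unless the value first falls below 1.5.

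This assumes that the Table 2 row and section 7 govern when liver and renal tests are done, and that an increase to a level means a rise from the entry value. On that reading a stable value triggers neither rule.

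Three stronger conclusions are not supported:
- That patients were left without protection: the other routes exist, and no affected patient is described.
- That week-12 liver fat data were lost or the comparison biased: 4.3 does not say whether imaging is still done after termination.
- That many patients fall in the creatinine band: the documents give no count among the 60, and it is probably small.

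No effect on power or on the estimate is claimed.

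**What to change.** **For the protocol text or a successor trial:**
- Mark liver and renal functions at week 8 in Table 2 and section 7, run on the blood already drawn.
- State in 4.3 that any on-treatment ALT or AST at or above 6 times the upper limit is repeated promptly, and again at about 4 weeks, at an unscheduled visit if needed. The prompt repeat matters because waiting 4 weeks for the next value is weak monitoring in itself.
- Align the creatinine limits, for example by excluding at 1.5 mg/dL or above, or by defining the stop as a stated rise from baseline.

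**For this trial,** which section 3.1 describes as conducted with 60 patients enrolled, a schedule change comes too late. Report by arm the number terminated under each 4.3 rule, the number with on-treatment ALT or AST at or above 6 times the upper limit, and the number who entered with creatinine of 1.5 to under 2.0 mg/dL.

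**Cost.** For this trial, one descriptive table. For the text, wording in 4.2, 4.3, section 7 and Table 2, one extra panel on existing blood, an occasional extra visit and possibly a few fewer eligible patients.

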5.1 Dietetic intervention

- ICR group: Participants in ICR group were instructed to ensure 2 successive days of fasting-mimicking and 5 days of recovery per week. On fasting-mimicking days, the participants were instructed to consume approximately 500 kcal/day and they were provided with plant-based meal replacement (ZhenBaiNian nutrition bar, Beijing Winlife Research Institute of Nutrition, Health, Food Science, and Technology, China) to improve adherence and ensured adequate intake of micronutrients. In the rest 5 days of recovery per week, participants were allowed to consume their usual diet. Main ingredients of this meal replacement are as follows:
  - Main ingredients: isomaltooligosaccharide solution, high-protein and high-fiber crispy grain (soy protein isolate, rice, polydextrose, calcium carbonate), Chia seed, resistant dextrin, coconut potato, salty vegetable grain, etc.

Table 1. Information of nutrition bar used in this trial			
	Per 100g	%NRV	

energy	355.4 kcal	18%
protein	15.4 g	26%
Fat	12.4 g	21%
Trans fats (acids)	0 g	
Polyunsaturated fatty acids	3.6 g	
carbohydrate	34.0 g	11%
dietary fiber	23.5 g	94%
sodium	261 mg	13%
vitamin A	565 µg	71%
vitamin D	2.5 µg	50%
vitamin E	8.05 mg	58%
Vitamin B1	1.30 mg	93%
Vitamin B2	1.30 mg	93%
Vitamin B6	1.30 mg	93%
Vitamin B12	0.80 µg	33%
vitamin C	67.7 mg	68%
nicotinic acid	13.50 mg	96%
folic acid	328 µg	82%
Pantothenic acid	3.17 mg	63%
Biotin	3.8 µg	13%
phosphorus	257 mg	37%
potassium	318 mg	16%
magnesium	72 mg	24%
calcium	433 mg	54%
iron	6.7 mg	45%
zinc	5.25 mg	35%
selenium	10.0 µg	20%
copper	0.44 mg	29%
fluorine	0.06 mg	6%
manganese	1.00 mg	33%
ω~ 6 Linoleic acid	1.6 g	
ω~ three α- linolenic acid	2.0 g	

Manufacturer: Beijing Wanlaikang Nutrition and Health Food Science and Technology Research Institute Co., Ltd

Product standard No.: Q/CPKWC 0085

> Food production license No.: SC10611141312769

 CCR group: Participants in CCR group were instructed to consume the prescribed calories (25 kcal / kg × [height (cm) – 100] kg) every day by eating conventional food without time restriction.

Both groups received dietary counseling from experienced nutritionists during the trial. Kitchen scales were distributed to participants, and they were encouraged to weigh food to ensure accurate reporting of their caloric intake. During the trial, all the participants were required to write daily dietary log. Using each log, nutritionists assessed their calorie intake each day based on the nutrient content shown on the Chinese Food Composition Table.Participants received face-to-face instruction or app messages every week to assess their adherence to the prescribed diet.

# 5.2 Physical activity

During the trial, all participants were required to maintain their exercise routines and record their daily steps using a unified pedometer (Redmi Smart Band, Xiaomi Corporation, China). The use of drugs affecting blood glucose and fatty liver were avoided.

- 6. Study outcomes
- 6.1 Primary outcome
- Change in liver fat content from baseline to 12 months

6.2 Secondary outcomes

- Change of weight
- Change of blood glucose: fasting blood glucose,2h postload blood glucose, HbA1c
- Change of liver enzymes: alanine aminotransferase, aspartate aminotransferase, γglutamyl transpeptidase
- Change of lipid profile: total cholesterol, triglyceride, high-density lipoprotein-cholesterol, low-density lipoprotein-cholesterol, free fatty acid

6.3 Other pre-specified outcomes

- Change of fat mass and lean mass measured by a bioimpedance analyzer
- Change of abdominal adiposity measured by MRI: visceral adipose tissue and subcutaneous adipose tissue
- Change of liver stiffness measured by liver transient elastography
- Change of insulin sensitivity: fasting insulin and HOMA-IR (fasting glucose in mmol/L x fasting insulin in  $\mu$ U/mL)/22.5)
- 7. Follow-up visits
- (1) Screening visit (V0): The purpose of this visit is to confirm subjects' eligibility and interest in the proposed study, and obtain informed consent, relevant medical history (including diabetes, fatty liver, alcohol drinking history, hepatitis history, drug use, etc.), physical measurements (weight, height, waist circumference and blood pressure), and laboratory measurements (OGTT, HbA1c, liver and renal functions, electrolytes, hepatitis markers, etc). H-Proton Magnetic Resonance Spectroscopy (H-MRS), MRI-Proton Density Fat Fraction (MRI-PDFF) and liver transient elastography were applied to evaluate the fatty liver. Body composition analysis and other examinations were performed. Relevant laboratory and imaging examination results within 2 weeks before screening can be approved.
- (2) Baseline visit (V1): The baseline follow-up was scheduled within 2 weeks after the screening period. Physical examination was conducted. Subjects will be required to record their diet and steps for 3 days before day 0 and the average of calorie consumption and steps will be used as baseline reference. Randomization will be conducted.
- (3) Follow up and termination visits (V2 V9): At each visit, diet and step records will be collected. At week 2, 4, 8 12, physical measurements, fasting glucose and adverse events will be recorded. Nutritionists will provide dietary advice and help subjects to keep calorie

restriction and a balance of nutrients. On this basis, liver and renal functions, electrolytes, fasting blood glucose and lipids profiles will be measured at week 4. At week 12 (termination visit), OGTT, H-MRS, MRI-PDFF, liver transient elastography and body composition analysis will be added. At week 1, 3, 6, 10, only telephone follow-up will be conducted.

(4) Post-intervention visit (V10): At 4 weeks after the intervention (week 16), body weight will be investigated by telephone.

	Screening	Baseline								Termin ation	Post- interve ntion
Visit	V0	V1	V2	V3	V4	V5	V6	V7	V8	V9	V10
Week	<-2	0	1	2	3	4	6	8	10	12	16
Day		0	7±3d	14 ± 7d	21 ± 3d	28±7d	42±3d	56±7d	70 ± 3d	84±7d	112±3 d
Inform consent	Х										
Randomization		Х									
Demographic	x										
information	~										
History about fatty liver and hyperglycemia	х										
Comorbidity and concomitant drug use	х										
blood pressure	Х	Х		Х		Х		Х		Х	
Height	Х									Х	
Weight	Х	Х		Х		Х		Х		Х	Х
Waist circumference	х	х		х		х		х		х	
Diet and steps records for 3 days		х									
OGTT	X									X	
HbA1c liver and renal	Х									Х	
functions	X					X				X	
Lipid profile	Х					Х				Х	
Fasting plasma glucose	Х			х		х		х		х	
Electrolytes	Х					Х				Х	
Routine blood test	Х					Х				Х	
Hepatitis markers and autoantibody	х										
Urinalysis	Х									Х	
Liver transient elastography	х									х	
Liver  H-MRS	Х									Х	
Liver MRI-PDFF	Х									Х	
Brain functional MRI	х									х	
Body composition	х									х	
Activity (steps)		Х	Х	Х	Х	Х	Х	Х	Х	Х	
Diet guidance		Х	Х	Х	Х	Х	Х	Х	Х	Х	
Blood sample		Х		Х		Х		Х		Х	
Urine and feces sample		х								х	

Table 2. Study visits and data collection

Adverse events		Х	Х	Х	Х	Х	Х	Х	Х	Х	
Distribute/Collect diet diary	х	х		х		х		х		х	
Distribute/Collect research food (only for ICR group)		х		х		х		х		х	

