# 9. Adverse events (AE)

### 9.1 Definition

Non-Serious Adverse Event (NSAE) refers to an unforeseeable medical condition that occurs during or after the treatment, or an event that makes the original condition worse. The occurrence of NSAE does not necessarily have a causal relationship with the intervention. Adverse medical conditions include symptoms (such as nausea and chest pain), physical signs (such as tachycardia and hepatomegaly) or abnormal examination results.

Serious adverse event (SAE) refers to the adverse event that meets one or more of the following criteria caused by intervention in screening method, treatment period, cleaning period or follow-up period:

1) Causing death;

- 2) Life-threatening injury;
- 3) Leading to longer hospitalization;
- 4) Causing continuous or obvious disability;
- 5) Congenital malformation/defect;

6) Major medical events that may cause injury to the subject or require medical intervention to prevent its occurrence.

Severity grading of non-serious adverse events:

1=mild (with symptoms or signs, but tolerable)

2=moderate (feeling unwell and affecting normal activities)

3=severe (inability to perform normal activities)

The unresolved NSAE at the end of the trial need to be followed up. The follow-up interval and duration depend on the medical needs. For the unsolved adverse events at the end of the trial or when the subjects withdraw from the study, the follow-up shall be conducted until the NSAE returns to normal, or until the investigator believes that further follow-up is not necessary. 9.2 Recording and assessment of adverse events

Attention should be paid to the collection of AE during the whole research process. The following are the variables that should be recorded for each AE: onset and stop time, severity, measurements, causal relationship with intervention, outcomes and whether it is a serious adverse event.

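### Section 7 and Table 2 disagree on when adverse events are recorded (four versus eight post-baseline contacts), and neither schedules an enquiry at the week-16 call

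*Combined protocol and SAP*

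**What the plan says.** Section 7, item (3), covers V2 to V9 and ties AE recording to four of those visits: "At week 2, 4, 8 12, physical measurements, fasting glucose and adverse events will be recorded". Of the remaining contacts it says: "At week 1, 3, 6, 10, only telephone follow-up will be conducted". Item (4) describes V10: "At 4 weeks after the intervention (week 16), body weight will be investigated by telephone".

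Table 2 has a row labelled "Adverse events". It is marked at V1 through V9 without a break and is blank at V0 and V10.

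Section 9.1 defines a non-serious AE as "an unforeseeable medical condition that occurs during or after the treatment", or an event that worsens the original condition. Its definition of a serious AE covers events "caused by intervention in screening method, treatment period, cleaning period or follow-up period". Section 9.2 adds a general instruction, "Attention should be paid to the collection of AE during the whole research process", and lists what is recorded for each event: "onset and stop time, severity, measurements, causal relationship with intervention, outcomes and whether it is a serious adverse event". Section 9.1 also requires non-serious events still open at the end of the trial to be followed up. Section 9.3 requires every serious event to be reported, related or not, and sets no visit limit.

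**The concern.** There are two separate problems.

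First, the text and the schedule table give different instructions on the same matter. A site working from section 7 would ask about AEs half as often after baseline as one working from Table 2. Mild and moderate events of a dietary intervention are short-lived and easily forgotten, so the recall interval affects how many are recorded.

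Second, the definition of a non-serious AE is wider than the schedule that feeds it. Events after the diet ends fall inside the definition, but no contact after week 12 has an AE question attached, although a call is made at week 16.

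The stated aim in section 2 covers the safety of intermittent restriction as well as its efficacy. With 30 participants per arm, a handful of unrecorded events could change the safety comparison.

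**Working it through.** The plan gives no count of AE contacts to reproduce, so the check compares the two schedules directly.

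**1. Contacts at which AEs are recorded**

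| Source | Weeks | Total | Post-baseline |
|---|---|---|---|
| Section 7 text | 2, 4, 8, 12 | 4 | 4 |
| Table 2, AE row | 0, 1, 2, 3, 4, 6, 8, 10, 12 | 9 | 8 |

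In the table but not the text: weeks 0, 1, 3, 6 and 10. In the text but not the table: none. Week 0 is the randomization visit, before any time on the diet, so the fair comparison is 4 with 8.

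A broken table row is an unlikely explanation. The AE marks run in unbroken sequence, while the rows for clinic measurements such as blood pressure and waist circumference skip the telephone weeks as expected.

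**2. Nominal intervals between enquiries, counted from week 0**

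- Section 7: 2, 2, 4, 4 weeks. Longest: 4 weeks.
- Table 2: 1, 1, 1, 1, 2, 2, 2, 2 weeks. Longest: 2 weeks.

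**3. Longest intervals the visit windows allow**

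The windows in Table 2 are V5 28±7 (days 21–35), V6 42±3 (39–45), V7 56±7 (49–63), V8 70±3 (67–73) and V9 84±7 (77–91). The longest interval is the latest day of the later contact minus the earliest day of the preceding one.

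- Section 7: V5 to V7, 63 − 21 = 42 days; V7 to V9, 91 − 49 = 42 days.
- Table 2: V5 to V6, 45 − 21 = 24 days; V6 to V7, 63 − 39 = 24; V7 to V8, 73 − 49 = 24; V8 to V9, 91 − 67 = 24.

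These are extremes: one contact at its earliest permitted day and the next at its latest.

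**4. After week 12**

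- AE enquiries scheduled after V9: 0 in the text, 0 in the table.
- Nominal time from V9 to V10: 112 − 84 = 28 days, or 4 of the 16 weeks after randomization (4/16 = 25%).
- The provision for unresolved events in section 9.1 applies to events already known at the end of the trial. It does not prompt a question about new ones.

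**The case against.** The strongest reply is that the plan does not confine AE collection to listed visits. Section 9.2 sets a study-wide duty and records onset and stop times, so an event between visits can be entered at the next contact. Section 9.3 makes all serious events reportable at any time. Section 5.1 adds weekly contact with participants. The telephone-only wording in section 7 may describe the mode of contact rather than exclude AE questions, and a site that works from Table 2 already asks at those calls.

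Much of this stands, and it rules out several stronger readings that a reader might infer:

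- **That between-visit events are missed.** The recording of onset and stop times contradicts this. What remains is weaker recall over a longer interval.
- **That serious events after week 12 cannot be collected.** Section 9.3 contradicts this. The serious-event definition adds little either way: section 7 applies the term follow-up to V2 to V9, so the follow-up period in section 9.1 need not mean weeks 12 to 16.
- **That recall under section 7 always spans four weeks or more.** Two of its four intervals are two weeks.
- **That under-recording makes the intermittent arm look safer.** The documents give no AE rates or recall data. The continuous arm restricts intake every day and may also have diet-related events, and in an open-label trial awareness of fasting days could raise reporting in the intermittent arm.

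The reply does not remove the contradiction between section 7 and Table 2. Nor does it supply a prompt after week 12: a general duty to collect depends on the site learning of the event, and the stated purpose of the weekly contacts in section 5.1 is to assess dietary adherence.

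**Conclusion.** The point holds in limited form. Section 7 and Table 2 set incompatible AE schedules, 4 against 8 post-baseline contacts, with longest nominal intervals of 4 and 2 weeks (at the limits of the windows, 42 and 24 days). Under both versions the last 4 of 16 weeks have no scheduled AE enquiry, although the non-serious definition extends past treatment and a call is already planned. The likely consequence is some under-recording: of mild and moderate events on the diet if section 7 is followed, and of new non-serious events in weeks 12 to 16 under either version.

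This rests on two assumptions: that recall of minor events worsens as the interval lengthens, and that participants do not reliably volunteer such events unasked. The documents do not allow the number of affected events, or any difference between arms, to be estimated. The primary outcome is not affected.

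**What to change.** 1. Reword section 7, item (3), so that AEs are recorded at every contact from V1 to V9, telephone calls included, as Table 2 already shows.
2. Mark V10 in the AE row of Table 2 and reword section 7, item (4), so that the week-16 call covers body weight and adverse events.
3. State week 16 as the end of the AE collection window, so that sections 7, 9.1 and 9.2 and Table 2 agree.

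Section 3.1 describes the trial as conducted between July 2020 and July 2021. If it is complete, the report should instead state which AE schedule was followed and limit the safety conclusion to the period actually covered.

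The cost is a short amendment and a few minutes on calls already planned, with no new visit. Recorded AE counts may be slightly higher.
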